5.4.3. Management of Dose-Limiting Toxicities or Other Urgent Situations

In all cases, investigators may employ any measures or concomitant medications, after discussion with the medical monitor (whenever possible), necessary to optimally treat the subject.

5.4.4. Follow-Up of Dose-Limiting Toxicities

Any DLT should be followed until it resolves to baseline or appears to have stabilized for a minimum of 4 weeks (eg, 28 days). During follow-up, subjects should be seen as often as medically indicated to assure safety.

5.4.5. Procedures for Cohort Review and Dose Escalation

Telephone conferences will be scheduled by the sponsor with study investigators in order to review cohort-specific data and overall safety data, to agree on dose escalation, adjudicate individual high-grade AEs as potentially dose-limiting, and guide other major study decisions.

5.4.6. Criteria and Procedures for Dose Interruptions of Study Drug

Treatment with INCAGN01949 in combination with standard immune therapies may be delayed up to 4 weeks (28 days) to allow for resolution of toxicity. **If an interruption or discontinuation is necessary, all study treatments should be interrupted or discontinued.**

Subjects may resume treatment if no medical condition or other circumstance exists that, in the opinion of the investigator, would make the subject unsuitable for further participation in the study. The treating investigator should contact the medical monitor to discuss the case of any subject whose treatment has been delayed for more than 4 weeks (28 days) before restarting treatment.

Instructions for dose interruptions are outlined in [Table 9](#). Individual decisions regarding dose interruptions of study drug should be made using clinical judgment and in consultation with the medical monitor (whenever possible), taking into account relatedness of the AE to the study drug and the subject's underlying condition. Adverse events that have a clear alternative explanation, or transient (\leq 72 hours) abnormal laboratory values without associated clinically significant signs or symptoms, may be exempt from dose-interruption rules.

Dose interruptions are permitted in the case of medical/surgical events or logistical reasons not related to study therapy (eg, elective surgery, unrelated medical events, subject vacation, and/or holidays). Subjects should be placed back on study therapy within 4 weeks (28 days) of the scheduled interruption, unless otherwise discussed with the medical monitor. The reason for interruption should be documented in the subject's study record.

Table 9: Criteria for Interruption and Restarting of Study Treatment

CTCAE Grade/Severity	Hold Treatment (Y/N)	Timing for Restarting Treatment	Dose Level for Restarting INCAGN01949	Dose Level for Restarting Immune Therapies	Treatment Discontinuation
1-2 (Mild to moderate)	No	Continue treatment at the discretion of the investigator.	N/A	NA	N/A
3 (Severe)	Yes	Toxicity resolves to Grade 0-1.	Restart same dose	Restart same dose	Toxicity does not resolve within 4 weeks (28 days) of last dose, except by approval of the medical monitor. OR Second occurrence of previously resolved Grade 3 AE.
4 (Life-threatening)	Yes	Permanent discontinuation, except by approval of the medical monitor. If continuing, toxicity must resolve to Grade 0-1.	Permanent discontinuation, except by approval of the medical monitor. If continuing, restart same dose	Permanent discontinuation, except by approval of the medical monitor. If continuing, restart same dose.	Permanent discontinuation for any severe or life-threatening event, except by approval of the medical monitor.

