5.4.9. Criteria for Permanent Discontinuation of Study Drug

The occurrence of unacceptable toxicity not caused by the underlying malignancy will be presumed to be related to study treatment and will require that the study treatment be permanently discontinued. Unacceptable toxicity is defined as follows:

- Grade 4 or life-threatening AEs, except with approval from the medical monitor.
- \geq Grade 2 ocular irAE.
- Occurrence of an AE that is related to treatment, in the judgment of the investigator or the medical monitor, and compromises the subject's ability to continue study-specific procedures or is considered to not be in the subject's best interest.
- Persistent AE requiring a delay of treatment for more than 4 weeks (28 days) unless a greater delay has been approved by the sponsor.

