Endocrinopathies	
Note: Subjects should be monitored for clinical signs and symptoms of hypophysitis, adrenal insufficiency (including adrenal crisis), and hyper- or hypothyroidism. Subjects may present with fatigue, headache, mental status changes, abdominal pain, unusual bowel habits, and hypotension, or nonspecific symptoms which may resemble other causes such as brain metastasis or underlying disease. Unless an alternate etiology has been identified, signs or symptoms of endocrinopathies should be considered immune-mediated.
 
For Grade 2 (mild to moderate new symptoms):
 
• In hypophysitis, treat with systemic corticosteroids, per institutional standard of care. When symptoms improve to Grade 1 or less, steroid taper should be started and continued over no less than 4 weeks. Replacement of appropriate hormones may be required as the steroid dose is tapered. 
Note: These suggested supportive care measures also apply to Grade 3 hypophysitis
 
• In hyperthyroidism, nonselective beta-blockers (eg, propranolol) are suggested as initial therapy.• In hypothyroidism, thyroid hormone replacement therapy, with levothyroxine or liothyronine, is indicated per standard of care. 
Note: Isolated hypothyroidism may be treated with replacement therapy without treatment interruption and without corticosteroids.
 
• Evaluate endocrine function and, as clinically indicated, consider pituitary scan.• For subjects with abnormal endocrine work-up, except for those with isolated hypothyroidism, consider short-term, high-dose corticosteroids (eg, methylprednisolone or IV equivalent) and initiate appropriate hormone replacement therapy.• For subjects with normal endocrine work-up (labs or MRI), repeat labs/MRI as clinically indicated. 
For Grade 3 or 4 (severe or new symptoms, new/worsening endocrinopathies, life threatening):
 
• Hypothyroidism may be treated with replacement therapy without treatment interruption and without corticosteroids.• In hyperthyroidism, treat with an initial dose of IV corticosteroid followed by oral corticosteroids. Consider initiation of systemic corticosteroids at a dose of 1-2 mg/kg per day of prednisone or equivalent, and initiate appropriate hormone replacement therapy. Once improving, gradually taper immunosuppressive steroids over ≥ 4 weeks.• In hypophysitis, treat with an initial dose of IV corticosteroids followed by oral corticosteroids. When symptoms improve to Grade 1 or less, steroid taper should be started and continued over no less than 4 weeks. Replacement of appropriate hormones may be required as the steroid dose is tapered.• For adrenal crisis, severe dehydration, hypotension, or shock: immediately initiate intravenous corticosteroids with mineralocorticoid activity.• Consult endocrinologist.• Consult medical monitor.

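### Table 9 conflicts with Section 5.4.9 on ocular immune-related events, with its own rows on severe events, and with Sections 5.4.6 and 5.4.9 on the 28-day limit

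*Protocol*

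**What the plan says.** **Table 9 (Protocol 5.4.6)** sets the action by CTCAE grade alone.

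- Grade 1-2: no hold, "Continue treatment at the discretion of the investigator", and discontinuation marked not applicable.
- Grade 3, labelled severe: hold, then restart at the same dose once "Toxicity resolves to Grade 0-1". Discontinue if "Toxicity does not resolve within 4 weeks (28 days) of last dose, except by approval of the medical monitor", or on a second occurrence.
- Grade 4, labelled life-threatening: "Permanent discontinuation for any severe or life-threatening event, except by approval of the medical monitor".

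**The text of 5.4.6** lets combination treatment be delayed by up to 28 days for toxicity. Beyond that, it asks the investigator to discuss the case with the medical monitor before restarting. It also allows clinical judgment on interruptions.

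**Section 5.4.9** says that unacceptable toxicity "will require that the study treatment be permanently discontinued". Its list includes "Grade 2 ocular irAE" (printed with a greater-than-or-equal sign) and "Persistent AE requiring a delay of treatment for more than 4 weeks (28 days) unless a greater delay has been approved by the sponsor". **Section 5.5.1** says subjects with unacceptable toxicity as defined in 5.4.9 must be withdrawn from study treatment.

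**Appendix B, Endocrinopathies**, says "hypothyroidism may be treated with replacement therapy without treatment interruption and without corticosteroids". This wording appears in the Grade 2 note for isolated hypothyroidism and again, for hypothyroidism generally, in the Grade 3 or 4 list.

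**The concern.** Table 9 is the page a site is likely to consult when a toxicity occurs, and it has no exception row or cross-reference for ocular events. The protocol treats these events as a special risk: a history of any grade is exclusionary (3.2), and Grade 2 or higher is a dose-limiting toxicity (Table 8). If Table 9 is read alone, a subject whom 5.4.9 requires to stop can stay on treatment.

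The wording of the Grade 4 row and the 28-day limit raise a different problem. Whether a subject with a Grade 3 event may restart can depend on which sentence the site applies.

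Enrollment has closed at 52 subjects, but treatment may continue for up to 24 months (4.1), so these rules still govern anyone on treatment. SAP 8.2.4 also tabulates interruptions and discontinuations due to adverse events, and those counts follow from the same instructions.

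**Working it through.** The plan gives no figure to reproduce. Three of the four points are a comparison of text; the 28-day limit needs a short calculation.

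**Side by side**

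| Event | Table 9 | Other passage | Can both be followed? |
|---|---|---|---|
| Ocular irAE, Grade 2 | No hold; investigator discretion | 5.4.9 and 5.5.1: mandatory permanent stop | Only by stopping |
| Ocular irAE, Grade 3 | Hold; restart at same dose on resolution | 5.4.9 and 5.5.1: mandatory permanent stop | Not if restarted |
| Any Grade 3 (severe) | Grade 3 row: hold, then restart | Table 9, Grade 4 row: discontinue for severe events unless the medical monitor approves | Not on the literal wording, without approval |
| Hypothyroidism, Grade 3 | Hold | Appendix B: may be treated without interruption | Yes, by holding |
| Hypothyroidism, Grade 4 | Discontinue unless the medical monitor approves | Appendix B: may be treated without interruption | Yes, by stopping or with approval |

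The ocular bullet in 5.4.9 carries no exception. The Grade 4 and prolonged-delay bullets beside it do.

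**The 28-day limit for Grade 3 events**

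Inputs: the limit is 28 days (Table 9, 5.4.6 text, 5.4.9), and the cycle is 14 days with a window of 3 days either side (Table 12, footnote a).

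Let *d* be the number of days from the last dose to the start of the delay. Count the limit in days after the last dose.

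- Table 9: limit = 28.
- 5.4.6 text and 5.4.9: limit = *d* + 28.
- Gap = (*d* + 28) − 28 = *d*.

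The protocol does not define when a delay starts, so *d* is an assumption:

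| Delay counted from | *d* | Limit under 5.4.6/5.4.9 | Gap from Table 9 |
|---|---|---|---|
| Last dose | 0 | Day 28 | 0 days |
| Missed dose, on schedule | 14 | Day 42 | 14 days |
| Missed dose, early end of window | 11 | Day 39 | 11 days |
| Missed dose, late end of window | 17 | Day 45 | 17 days |

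Example: a Grade 3 event resolves, and treatment could restart, on Day 35 after the last dose. Under Table 9, 35 > 28, so the subject discontinues unless the medical monitor approves otherwise. Counted from a missed dose on Day 14, the delay is 35 − 14 = 21 days, which is within 28 and permitted.

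The gatekeeper beyond 28 days also varies: medical monitor approval in Table 9, discussion with the medical monitor in the 5.4.6 text, and sponsor approval in 5.4.9.

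**The case against.** The best defense is that the specific rule governs the general one. Section 5.4.9 is mandatory, 5.5.1 points to it, and Table 9 leaves Grade 2 to discretion without ordering continuation. A site that stops for a Grade 2 ocular event complies with everything. That is correct, so the breach runs one way only. But no passage states which rule takes precedence, and the latitude for judgment in 5.4.6 cannot displace a rule that subjects must be withdrawn.

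The stray reference to severe events can be called editorial, since Grade 3 has its own row and the Grade 4 row allows medical monitor approval. It is still the literal text of a stopping rule.

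On the clock, the gap disappears if delay is counted from the last dose. The limit in Table 9 sits in the Grade 3 row alone and can be waived. The difference in approver may be partly nominal, since SAP 9.1.1 places the study medical monitor on a committee it describes as internal to the sponsor. These points limit the size of the problem but do not supply a definition of delay or a single approver.

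On hypothyroidism, Appendix B is permissive, Section 5.4.7 calls such measures suggested, and the Grade 3 or 4 list ends with consulting the medical monitor. That reduces the item to a tension.

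A reader might infer further conflicts that the documents do not support:

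- **Grade 2 pneumonitis.** Table 8 makes it a dose-limiting toxicity, but under 5.4.2 that status drives cohort decisions, and Appendix B gives no hold or stop instruction for it. Nothing contradicts Table 9.
- **A second Grade 3 occurrence.** Table 9 stops treatment and the 5.4.9 list does not name it. Silence is not an opposite rule, and 5.4.9 has a general bullet on related events that may apply.
- **A 28-day limit in Appendix B.** There is none.

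**Conclusion.** The point holds in four parts of unequal weight.

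1. **Ocular immune-related events, Grade 2 or higher.** This is a firm conflict and enough by itself to require correction. Continuing at Grade 2, or restarting after Grade 3, follows Table 9 and breaches 5.4.9 and 5.5.1.
2. **Severe events.** Table 9 contradicts itself on the literal wording. The fault is editorial in origin but lies in a stopping rule.
3. **The 28-day limit for Grade 3 events.** Start point and approver differ. The gap is 0 days if delay runs from the last dose and about 14 days (11 to 17) if it runs from the missed dose. A fixed 14-day discrepancy should not be inferred, because it rests on a definition that the protocol does not give.
4. **Grade 3-4 hypothyroidism.** A lesser tension, because Appendix B is permissive.

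The parts should not be turned into a count of conflicting event types: a clock and a word are not events. Nor do the documents show that the SAP 8.2.4 tables are compromised. Those tables are descriptive, Protocol 9.3 plans no formal tests, and nothing shows that sites have read the rules differently. The case for acting is the protection of subjects still on treatment.

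**What to change.** Reconcile Table 9 with Sections 5.4.6, 5.4.9 and 5.5.1 and Appendix B on these four points:

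- one instruction for ocular immune-related events, the same in Table 9 and 5.4.9;
- consistent use of the word severe across the Grade 3 and Grade 4 rows;
- one defined start point and one approver for the 28-day limit, used in all three places;
- a cross-reference between Table 9 and Appendix B for hypothyroidism.

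Which clinical rule applies in each case is for the sponsor's clinical team to decide.

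The cost is protocol wording, by amendment or clarification letter to sites. No new procedures, subjects or analyses are needed.

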5.4.7. Management of Immune-Related Adverse Events

Nivolumab and ipilimumab are immune checkpoint inhibitors and are known to induce irAEs. INCAGN01949 is an immune modulator that may enhance the activity of other immunotherapies and therefore may also exacerbate any irAEs associated nivolumab and ipilimumab. Adverse events of a potential immunologic etiology or irAEs may be defined as an AE consistent with an immune phenomenon associated with drug exposure **after all other etiologies have been ruled out**. Immune-related AEs may be expected based on the nature of the study treatment, their mechanism of action, and reported experience with these and other immunotherapies. Special attention should be paid to AEs that may be suggestive of potential irAEs. An irAE can occur shortly after the first dose or several months after the last dose of treatment. Suspected irAEs should be discussed with the medical monitor when possible.

Subjects should receive appropriate supportive care measures as deemed necessary by the treating investigator. Suggested supportive care measures for the management of drug-related AEs with potential immunologic etiology are outlined in [Table 10](#). Detailed supportive care guidelines for specific irAEs can be found in [Appendix B](#). Nivolumab and ipilimumab are approved therapies and have specific irAE management guidelines within their package insert; the treating investigator may use labeled guidance or institutional guidelines for the management of irAEs if preferred. For each AE, attempts should be made to rule out other causes, including but not limited to metastatic disease or bacterial or viral infection, which might require specific supportive care.

Table 10: Supportive Care Guidelines for Immune-Related Adverse Events

CTCAE Grade/Severity	Supportive Care ^a
1 (Mild)	
Monitor symptoms and provide symptomatic treatment.
2 (Moderate)	
Monitor symptoms and provide symptomatic treatment.Consider consultation with specialists as necessary.Consider systemic corticosteroids per institutional standard of care.
3-4 (Severe to life-threatening)	
Monitor symptoms and provide symptomatic treatment.Consider consultation with specialists as necessary.Administer corticosteroids per institutional standard of care.More potent immunosuppressive therapies should be considered for events not responding to systemic steroids after discussing with the medical monitor.Study treatment may be permanently discontinued for clinically significant or severe irAEs, or for events where steroid course cannot be tapered below 7.5 mg/day prednisone or equivalent to manage symptoms.

^a Detailed supportive care guidelines for specific irAEs can be found in [Appendix B](#).

5.4.8. Management of Infusion Reactions

[Table 11](#) shows treatment guidelines for subjects who experience an infusion reaction associated with administration of study treatment. Signs and symptoms usually develop during or shortly after drug infusion and generally resolve completely within 24 hours of completion of infusion. Nivolumab and ipilimumab are approved therapies and may have specific infusion reaction management guidelines within their package insert; the treating investigator may use labeled guidance or institutional guidelines for the management of infusion reactions if preferred.

Table 11: Infusion Reaction Treatment Guidelines

CTCAE Grade	Treatment	Premedication at Subsequent Dose Administration
Grade 1: Mild reaction; infusion interruption not indicated; intervention not indicated.	Increase monitoring of vital signs as medically indicated until the subject is deemed medically stable in the opinion of the investigator.	None.
Grade 2: Requires infusion interruption but responds promptly to symptomatic treatment (eg, antihistamines, NSAIDs, narcotics, IV fluids); prophylactic medications indicated for \leq 24 hours.	
Stop infusion and monitor symptoms. Additional appropriate medical therapy may include but is not limited to the following:
 
 • IV fluids • Antihistamines • NSAIDs • Acetaminophen • Narcotics 
Increase monitoring of vital signs as medically indicated until the subject is deemed medically stable in the opinion of the investigator.
 
If symptoms resolve within 1 hour of stopping drug infusion, the infusion may be restarted at 50% of the original infusion rate. Otherwise, dose administration will be held until symptoms resolve, and the subject should be premedicated for the next scheduled dose.
 
Subjects who develop Grade 2 toxicity despite adequate premedication should be permanently discontinued from further study treatment.
	
Subject may be premedicated 1.5 hours (\pm 30 min) before infusion with the following:
 
 • Diphenhydramine 50 mg orally (or equivalent dose of antihistamine). • Acetaminophen 500-1000 mg orally (or equivalent dose of antipyretic).
Grade 3: Prolonged (ie, not rapidly responsive to symptomatic medication and/or brief interruption of infusion); recurrence of symptoms following initial improvement; hospitalization indicated for other clinical sequelae (eg, renal impairment, pulmonary infiltrates).	
Stop infusion.
 
Additional appropriate medical therapy may include but is not limited to the following:
 
 • IV fluids • Antihistamines • NSAIDs • Acetaminophen • Narcotics • Oxygen • Pressors • Corticosteroids • Epinephrine 	No subsequent dose.
Grade 4: Life-threatening; pressor or ventilatory support indicated.	
Increase monitoring of vital signs as medically indicated until the subject is deemed medically stable in the opinion of the investigator.
 
Hospitalization may be indicated.
 
Subject is permanently discontinued from further study treatment.
	

Note: Appropriate resuscitation equipment should be available in the room and a physician readily available during the period of drug administration.

5.4.9. Criteria for Permanent Discontinuation of Study Drug

The occurrence of unacceptable toxicity not caused by the underlying malignancy will be presumed to be related to study treatment and will require that the study treatment be permanently discontinued. Unacceptable toxicity is defined as follows:

- Grade 4 or life-threatening AEs, except with approval from the medical monitor.
- \geq Grade 2 ocular irAE.
- Occurrence of an AE that is related to treatment, in the judgment of the investigator or the medical monitor, and compromises the subject's ability to continue study-specific procedures or is considered to not be in the subject's best interest.
- Persistent AE requiring a delay of treatment for more than 4 weeks (28 days) unless a greater delay has been approved by the sponsor.

5.5. Withdrawal of Subjects From Study Treatment

5.5.1. Withdrawal Criteria

A subject may choose to withdraw from the study treatment at any time or be withdrawn from the study treatment by the investigator or sponsor, if the subject is noncompliant with the study requirements. If a subject is withdrawn from study treatment, then every reasonable effort should be made to determine the reason for withdrawal, and this information should be recorded in the eCRF.

Subjects **must** be withdrawn from **study treatment** for the following reasons:

- The subject becomes pregnant.
- Consent is withdrawn. Subjects may choose to withdraw from the study at any time without penalty of jeopardizing their health care or loss of benefits to which the subject is otherwise entitled.
Note: Consent withdrawn means that the subject can no longer be followed and no additional data can be collected. Subjects may choose to discontinue study treatment and remain in the study to be followed for safety through the safety follow-up period.
- Further participation would be injurious to the subject's health or well-being, in the investigator's medical judgment.
- Unacceptable toxicity (see Section 5.4.9). Subjects with unacceptable toxicities must be withdrawn from study treatment but will continue in the follow-up phase of the study (see Section 6.4).
- The study is terminated by the sponsor.
- The study is terminated by the local health authority, IRB, or IEC.
- The subject has received 24 months of treatment with study drug.

A subject **may** be discontinued from **study treatment** as follows:

- Confirmed radiographic progression of disease per RECIST v1.1 (see Section 7.7.1). A subject may be granted an exception to continue on treatment with confirmed radiographic progression if clinically stable or clinically improved (see Section 7.7.1). **Note:** For unconfirmed progression, see Section 7.7.1.
- If, during the course of the study, a subject is found not to have met eligibility criteria (see Section 3), the medical monitor, in collaboration with the investigator, will determine whether the subject should be withdrawn from the study.
- If a subject is lost-to-follow-up or noncompliant with study procedures or study treatment in the investigator's opinion, the sponsor should be consulted for instruction on handling the subject.

